Screening Visit (SV): This in-person visit will be conducted at NBoC. It will include written informed consent, questions about demographics and confirming eligibility, a taste test of the frozen blueberries and dried dates, and a seated blood pressure measure to determine eligibility.

Wash-Out (WO): The Wash-Out will be the 1-2 week period leading up to the Baseline Visit. Participants will be asked to avoid all anthocyanin-rich foods for at minimum 1 week before baseline.

Baseline Visit (BV): After confirming eligibility and signed consent form and orally re-affirming consent, participants will complete fasting blood draw, spot urine collection, questionnaires, physical assessments, and set-up with a 24-hour ambulatory blood pressure monitor and Holter monitor. After successful completion of all BV data collection, participant will be randomized using REDCap. Participants will be given at least a 1-month supply of assigned fruit. They will also receive various handouts for compliance and adherence, tracking intake and falls, reporting unexpected events, and fruit pick-up.

Intervention (INT): Participants will receive a weekly email check-in from BV to FV to measure self-reported compliance with consuming study fruit and avoiding other anthocyanin-rich foods. The questionnaire will also include a section on reporting falls, as defined by the protocol. The purpose of the compliance questionnaire is to maintain rapport and improve adherence. If a participant does report a fall, study staff will call the participant within 3 days to administer the Fall Follow-Up Questionnaire. Additional fruit pick-ups will occur as needed.

Follow-Up Visit (FV): Participants will have an in-person visit at Week 12 after BV to re-do all BV assessments including phlebotomy, questionnaires, and physical function testing. Study staff will debrief with participants and provide some individualized results from the trial.

Table 2. Data collection schedule.

Study Visit Timeline	Visit 1 Screening (Week -2+)	Visit 2 Baseline (Week 0)	Week 4	Week 8	Visit 3 Week 12
Consent	X				
Demographic and medical questionnaires	X				
Vital signs	X				
Taste test	X				
24-hour electrocardiographic monitoring		X			X
24-hour ambulatory blood pressure monitoring		X			X
Fasting blood draw and spot urine		X			X
Randomization		X			
Fruit pick-up		X	X	X	
Compliance and STURDY questionnaires			X	X	X
Seated and standing blood pressure measures and anthropometrics		X			X
Physical function		X			X

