Adherence. Study staff will remind participants about the importance of adherence at the BV and any in-person or phone contacts. Various tools will be used to measure and promote adherence. Participants will receive various tracking tools, instructions, and ideas for consuming their assigned fruit. Participants will complete a short questionnaire on a weekly basis to self-report intake of assigned fruit, intake of any of the anthocyanin-rich foods to avoid, and incidence of falls. If participants are unable to complete the questionnaire remotely, study staff will administer by telephone. If participants missed >2 servings or consumed >1 serving of a restricted food, study staff will provide a follow-up counseling telephone call, text, or email, at participant discretion.

Participants will also be asked to return their containers of fruit at subsequent food pick-ups or at the FV. This will be used to measure compliance based on the weight/amount of leftover fruit since the last distribution.

Symptoms and adverse events. Study staff will collect information on symptoms and adverse events when reported by participants during the study and at the FV. Adverse events will be recorded. Serious adverse events will be recorded and reported to the PI and the BIDMC CCI.

8. Quality Assurance and Quality Control

The investigative team understands the critical importance of collecting complete, high-quality data and developing procedures to accomplish this important objective. Core activities include:

- Standardization - maintaining common study documents (protocol, MOP, case report forms) with special efforts to minimize version control issues.
- Training – developing training procedures led by experienced investigators and license holders, developing and implementing certification procedures and performance metrics, and conducting annual training.
- Robust data systems – implementing web-based data entry system through REDCap; using off-site data storage with automated back-up systems; checking logic and consistency of data between forms and over time.

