Participants that share a residence will be randomized as a household. That is to say, the second participant from the same household enrolled in the study will not be randomized, but rather automatically assigned to the study fruit that their spouse was assigned. This approach is intended to prevent cross-contamination and promote adherence and statistical plans will account for clustering if multiple household members are enrolled.

In both arms, participants are asked to avoid other anthocyanin-rich foods, including blackberry, cherry, concord grape, cranberry, currant, eggplant, plum, purple potato, red and black raspberry, red cabbage, red wine, rhubarb, and strawberry.⁽⁴⁰⁾ Participants will be provided a list of foods to avoid. They will also receive counseling and materials at the BV and throughout the study on ways to track and incorporate the assigned fruit. All participants will also be asked to maintain their 'usual' lifestyle throughout the 12-week period. This includes restricting changes to their exercise, diet, medication use, and other behaviors.

11. Safety

Safety monitoring

The study will actively monitor participant safety. One aspect of safety monitoring is to evaluate screenees to determine whether it is safe for them to participate. Key safety related eligibility criteria are the exclusion of persons with (a) an intolerance or allergy to blueberries or dates or (b) allergy to tree nuts, peanuts, soy, or milk products. The dried dates procured for the study are purchased from a supplier that also handles tree nuts, peanuts, soy, and milk products.

A second aspect is monitoring enrolled participants for safety issues potentially related to the study. Surveillance for serious adverse events and other relevant clinical events will occur by questionnaire and contact with participants. If a participant develops a medical problem, the safety of continuing or resuming the study will be ascertained by the PI and other clinical study team members.

In addition, blood pressure values at the SV, BV, and FV will be compared to the alert values based on average seated measurement. All participants with an elevated seated blood pressure measurement (SBP >180 or DBP >110 mm Hg) should be asked if they have the following symptoms: headache, vision change, chest pain, shortness of breath, or change in urine color. Study physician and/or PCP will be notified as necessary.

Table 3. Blood pressure alert values.

Issue	Action

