This trial will also be advised by an independent safety monitor. [name], director of continuing medical education at the West Roxbury Veterans Affairs Medical Center, will serve as safety monitor. Recurring meetings between [name], the study PI, and the study research coordinator will be held at least every 6 months to discuss any safety concerns and review all adverse events.

Potential risks

This study should not involve any major risks to screenees or participants and represents minimal risk above usual activities. Both dates and blueberries are widely consumed, readily commercially available, and (as whole fruits) considered healthy food choices. However, there are some potential risks associated with participation in this study, which are as follows:

- Participants may be uncomfortable with certain sensitive questions or questionnaires
- Bruising and a rare chance of local infection from venipuncture to collect blood samples could occur
- Participants may experience transient dizziness during measurement of orthostatic blood pressure
- Application of ABPM and ambulatory electrocardiographic monitoring may disrupt sleep
- There might be loss of confidentiality and privacy

Adverse event surveillance and reporting procedures

An adverse event is defined by the OHRP as “Any untoward or unfavorable medical occurrence in a human subject, including any abnormal sign,... symptoms, or disease, temporally associated with the subject’s participation in the research, whether or not considered related to the subject’s participation in the research.” The National Institute on Aging defines serious adverse events as any adverse event that:

- Results in death,
- Is life-threatening or places the participant at immediate risk of death from the event as it occurred,

- Requires or prolongs hospitalization,
- Causes persistent or significant disability or incapacity,
- Results in congenital anomalies or birth defects,
- Is another condition which investigators judge to represent significant hazards

Surveillance for SAEs and other relevant clinical events that may be associated with study participation will occur at in-person and telephone visits. In addition to the fixed time points, participants may report events in other settings, such as telephone contacts. The PI will review completed forms, will classify the event according to several dimensions (expectedness, relatedness to participation in the trial, and type), and take appropriate action.

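### The Safety section promises active surveillance by questionnaire and at fixed visits, but Section 7 as described leaves non-fall events before Week 12 to participant reports and incidental contact

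*Protocol*

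**What the plan says.** Section 11 (Safety monitoring) opens with a commitment: "The study will actively monitor participant safety". It then names the route: "Surveillance for serious adverse events and other relevant clinical events will occur by questionnaire and contact with participants". Later in the same section, under Adverse event surveillance and reporting procedures, the route is given as visits: "Surveillance for SAEs and other relevant clinical events that may be associated with study participation will occur at in-person and telephone visits". The next sentence separates those visits from spontaneous reports: "In addition to the fixed time points, participants may report events in other settings, such as telephone contacts".

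Section 7 describes what is done. In the contact schedule, the intervention period consists of one recurring contact: "Participants will receive a weekly email check-in from BV to FV to measure self-reported compliance" with the study fruit and the food restrictions, plus a section on falls. The stated purpose is rapport and adherence. The Adherence paragraph lists the content again: participants complete a short form "on a weekly basis to self-report intake of assigned fruit, intake of any of the anthocyanin-rich foods to avoid, and incidence of falls". The rule for adverse events is in the paragraph on symptoms and adverse events: "Study staff will collect information on symptoms and adverse events when reported by participants during the study and at the FV".

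**The concern.** The two sections describe different systems. Section 11 describes prompted surveillance at set times, with participant reports as an extra. Section 7 describes participant reports, with one set time at the end. A coordinator who follows Section 7 to the letter would ask every participant about falls each week and would not ask about any other health event until Week 12.

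Three features of the trial make this worth settling. The participants are aged 70 or older, and the protocol itself expects medical events in this group over the study period. Section 11 has the principal investigator and clinical team judge whether it is safe to continue when a medical problem develops, which they can do only if they hear of it. And Section 9 (Masking) says that neither participants nor the research coordinator are masked, so what is volunteered, and what is written down, may depend on the assigned fruit. A uniform prompt reduces that dependence.

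**Working it through.** The protocol gives no figure to reproduce. The check sets the promised routes against the described contacts between the baseline visit and Week 12.

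**Promised in Section 11**
- Surveillance by questionnaire.
- Surveillance at in-person visits.
- Surveillance at telephone visits.
- Spontaneous reports in other settings, in addition to the above.

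**Described in Section 7, Table 2 and Section 10**
- *Questionnaire.* The weekly form has three topics: assigned fruit, restricted foods, falls. Described items on other health events: 0. The sleep, quality-of-life, incontinence and dietary questionnaires are given at baseline and Week 12 only and are not presented as adverse-event instruments.
- *In-person visits.* Table 2 has Screening, Baseline, Week 4, Week 8 and Week 12. Weeks 4 and 8 carry fruit pick-up and the compliance and STURDY (falls) questionnaires. No row is for adverse events, and nothing says that staff ask about events at a pick-up. Week 12 is the only fixed time point after randomisation at which events are said to be collected: 1.
- *Telephone visits.* Scheduled after randomisation: 0. The calls that are described all depend on something else: the form cannot be completed remotely, adherence counselling is needed (where telephone is one of three modes), a fall is reported, or a result needs urgent attention.
- *Spontaneous reports.* These are supported by a baseline handout on reporting unexpected events. They are the one route that both sections describe in the same way before Week 12.

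**Scale**
- Weekly forms described without a general health item: 12 per participant × 70 participants = 840.
- Longest interval from randomisation to the fixed enquiry: 12 weeks × 7 days = 84 days. This bounds the recall period for an event that has not come to light by another route. It does not mean that staff have no contact with the participant for 84 days.

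So of the three promised routes, the telephone visits have no counterpart in Section 7. The questionnaire route is described for falls only, and the in-person route is met once, at Week 12.

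**The case against.** The strongest reply is that the weekly form is only summarised. The form, the other case report forms and the manual of procedures are not shown. Section 11 says that surveillance uses questionnaires and that the principal investigator reviews completed forms, so a prompt may exist. This stands: the finding is a contradiction within the protocol and not proof that no one asks.

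A second reply is that other contacts will catch much of what matters. More than 2 missed servings trigger a call, text or email from staff. An intolerance that stops consumption, or a hospital stay of several days, would often have that effect. Participants also taste both fruits at screening and collect fruit during the study. This partly stands. Those contacts make capture more likely, but they are set up for adherence, and an event that does not interrupt fruit intake does not trigger them.

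A third reply is that the risk is low: widely eaten whole fruits for 12 weeks, relevant allergies excluded, laboratory safety panels reviewed at baseline and follow-up, and an independent safety monitor. This limits the weight of the point but does not remove the contradiction.

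A reader might also infer more than the documents support:
- *That reactions to the fruit are never asked about after randomisation.* Section 7 has staff collect symptoms and adverse events at Week 12.
- *That the comparison of safety between fruits is biased toward no difference.* The protocol specifies no such comparison, and unmasked reporting could shift counts in either direction.
- *That participants who drop out are never asked.* The protocol describes no withdrawal enquiry, but it does not rule one out, and it gives no attrition rate and no reasons for dropping out.
- *That the 7-day reporting period for serious events is at fault.* It runs from when the coordinator learns of the event and would read the same after the change proposed here.

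**Conclusion.** The inconsistency holds. Section 11 promises active surveillance at fixed times by questionnaire, in person and by telephone. Section 7, as described, delivers one fixed enquiry about non-fall events after randomisation, at Week 12. Before then, such events reach the study through participant-initiated reports or incidental contact. The consequence is that ascertainment may be incomplete and may differ by arm. The documents establish neither the amount nor the direction.

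The size is minor to moderate. This rests on the protocol's description of the study as minimal risk, on the partial safeguards above, and on reading the two descriptions of the weekly form as complete. If the form already carries a general health item, only the wording needs repair.

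**What to change.** - Add one general item to the existing weekly questionnaire: any new symptom, reaction to the fruit, medical problem, emergency visit or hospital stay since the last questionnaire. A yes leads to staff follow-up through the contact process already in place.
- Ask the same item when a participant withdraws.
- Add an adverse-event row to Table 2 and show there that the questionnaire is weekly. The table now marks it at Weeks 4, 8 and 12 only.
- Reconcile the intervention, adherence and adverse-event paragraphs of Section 7 with both surveillance statements in Section 11. Either schedule the telephone visits or remove the reference to them.
- If the forms or the manual of procedures already contain such a prompt, say so in Section 7.

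The cost is one question in REDCap, some extra follow-up calls by existing staff, and more minor events on record.
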